6.1.4. Handling and dispensing of study medication

advanceCOR will send the investigational medicinal product to individual study sites. The Investigator or member of his team if this task is delegated will sign the Drug Receipt Form confirming receipt of clinical supplies for the study and provide assurance that the investigational product will be handled and stored properly. It is the responsibility of the Principal Investigator to ensure that investigational product is only distributed to trial participants. The investigational product must be dispensed by authorised personnel only. The Principal Investigator will ensure that the investigational product is stored in accordance with the environmental conditions (temperature, light, and humidity) as determined by advanceCOR. The investigational product shall be stored in a temperature-controlled freezer at -20 to -90°C in a secured area according to local regulations. If

concerns regarding the quality or appearance of the investigational product arise, do not dispense the investigational product and contact advanceCOR immediately.

6.1.5. Drug Accountability and Return and Destruction of Investigational Product

advanceCOR GmbH will supply a Drug Accountability Form, to be kept up-to-date by the Investigator.

At the Study Centre

Used /partially used vials*	Disposal at site according to local policy.
Drugs left unused / expired	Return to advanceCOR GmbH, preferably in the original package, a Drug Return Record Form must be completed.

*Used/partially used vials are accounted for in the Drug Accountability Form and therefore do not need their disposal accounted for separately (nor certificates of disposal) as it is inherent in the 'use' of the vials.

6.1.6. Treatment Administration

Revacept/placebo will be administered once per patient by intravenous injection as described in the handling instructions of the study medication. One patient dose is prepared by combining 3 IMP vials of a single kit box. Please equilibrate all vials of a kit box to room temperature before combining them in a 50 ml syringe pump. An in-line filter rated for syringe pump use must be inserted in the syringe pump infusion line. Infusion of IMP should be for 20 minutes.

6.1.7. Randomisation

Patients will be assigned to a treatment group by web-based online randomisation. Each patient will be allocated to one of the three treatment arms using a minimised randomisation method in order to balance potential prognostic factors between individual treatment arms. The following stratification factors will impact on treatment allocation:

- (1) Patient has received anti-platelet therapy with aspirin or clopidogrel prior to screening
 - No
 - Yes
- (2) Patient has received statin therapy prior to screening
 - No
 - Yes
- (3) Degree of carotid stenosis (ECST criteria)
 - 50-70%
 - > 70%

Once a patient is found to fulfil all eligibility criteria of the study the patient's identification number and details on concomitant medication are submitted to a web-based online randomisation program accessible at:

<https://www.randomizer.at/random/web/login.php>

All trial staff involved in patient randomisation will receive their log in data for the program after a short introduction to the system. In order to randomise a new patient, select "randomise" in the control panel on the left, enter the patient number (numeric format, including centre specific prefix, e.g. 01-005), select the applicable stratification

factors and click "randomise".

In case a reduced set of medication kit boxes is available at the study centre (e.g. due to damage or expiry of trial medication), you may tick option "reduced set of treatments", select "next", highlight all **unavailable** kit box numbers and then click on "randomise".

After successful randomisation of a patient, the web-based online system will send a confirmation email to the person who randomised the patient which contains the patient-specific random kit box number. This confirmation is to be printed, dated, signed and filed in the Investigator Site file.

Please check the number of remaining IMP kit boxes after each patient enrolment and make sure to request additional supplies as soon as less than 10 kit boxes remain, or earlier, in case of high recruitment rates.

6.1.8. Revision of randomisation

Randomisations may be revised if incorrect data have been entered into the web-based randomisation system, if the random kit box number allocated is not available for any reason or if a patient discontinued study participation prior to completion visit 5. In order to revise or reject a patient's randomisation, the following procedure shall be followed:

Revision of patient number

If a wrong patient number was entered into the web-based randomisation system, the entry may be corrected by logging onto the system, choosing "revise randomisation" in the control panel on the left, entering the randomisation number and corrected patient number in the corresponding fields, selecting "change patient-ID" from the drop down menu and providing a reason for the change.

A randomisation must be rejected (and repeated if applicable) for any of the following reasons:

- The medication kit box of the allocated random number is not available for any reason (was damaged, already used etc.)
- A wrong selection was made when entering the patient's stratification factors (degree of stenosis and/or previous Aspirin therapy)
- A patient may be replaced for example because he/she did not complete visit 5

Rejection of randomisation can only be performed by the Sponsor. Please contact the Monitor or the advanceCOR Clinical Development Department as soon as possible.

6.2. Blinding/Unblinding

Emergency unblinding is performed using the web-based online randomisation tool. The Investigator should ensure that the code is broken only in accordance with the protocol. For unblinding, the Investigator should note the date, time and reason for unblinding in the patient notes and promptly inform the Monitor or Sponsor and the Coordinating Investigator of any premature unblinding (e.g. accidental unblinding, unblinding due to a serious adverse event) of the investigational product(s).

6.3. Supportive Care

The accompanying medication will encompass the entire spectrum medication for treatment of carotid stenosis, TIA, amaurosis fugax and stroke in accordance with the corresponding guidelines. The investigation plan will in no way present restrictions in this sense, see section 5.2.2 for prohibited treatments. Most importantly, this clinical trial will not delay or hinder carotid artery desobliteration. Any required change of concomitant medication in accordance with clinical needs will be documented.

6.4. Treatment Compliance

The study site must keep a record of all study medication dispensed or disposed off throughout the study no matter whether on purpose or accidentally. Subjects who are noncompliant to receiving study medication will be discontinued from study treatment and are offered a follow-up visit including all assessments scheduled for visit 3 and 5.

7. STUDY ASSESSMENTS AND PROCEDURES

7.1. Procedures by visit

Informed consent must be obtained prior to any study procedure that would not have been performed as part of normal subject care. Additional follow-up visit(s) will be required every 4 weeks until all study related toxicities resolve to baseline, stabilise or are deemed irreversible, whichever is longer. Any additional medical testing and procedures, whether more frequent or in addition to those described, should be performed as medically indicated.

Procedure	Visit	Screening	Randomisation	Treatment (T)	T + 24 hrs (± 22 hrs)	T + 3 d (-69 hrs/+5d)	CEA + 24 hrs (± 24 hrs)	Follow Up		Protocol section	
		1		2	3	4	5	T+ 3 m (± 1 m)	T + 12 m (± 1 m)		6
Informed consent		X									4.3
Randomisation			X								6.1.7
Study medication (Revacept or placebo)				X							6
CEA or other intervention						X ^f					7.2.3
CEA / intervention outcome							X ^f				
Anamnesis		X									7.2.1
Concomitant medication		X		X	X	X	X	X			
Physical examination		X ^r		X	X	X ^r	X ^r	X			7.2.2
Adverse events				X	X	X	X	X			7.2.5 and 8
MRS, Barthel Index				X ^r				X			7.2.4
NIH Stroke Scale				X ^r			X ^r	X			
Clinical outcome								X	X		7.2.6
TCD		X			X						7.2.7
Electrocardiogram		X ^r			X		X ^r	X			7.2.8
DWI-NMR		X ^{a,r}					X				7.2.9
Laboratory Tests	Biochemistry	X ^r			X ^r		X ^r	X			7.2.10
	Haematology / Bleeding	X ^r			X ^r		X ^r	X			7.2.11
	Coagulation	X ^r			X ^r		X ^r	X			7.2.10
	Urinalysis	X ^r			X ^r		X ^r	X			7.2.13
	In vitro bleeding time (PFA100 / PFA200) and aggregation*				X*	X*	X*		X*		7.2.12
	Pregnancy test	X									7.2.14
	Pharmacokinetics (selected patients)				X ^b	X ^c	X ^d		X ^e		7.2.15
	Anti-drug antibodies				X				X		

^r routine assessment / blood sampling

* where feasible

^a eligible patients only

^b drawing times: t0 prior to IMP administration, t 0.5h 30 mins (± 5 mins) after start of IMP infusion, t 6h: 6 h (± 1 hr) after start of IMP infusion

^c drawing time: t24h (± 4 hrs) after start of IMP infusion

^d drawing time: t3d (± 48hrs) after start of IMP infusion

^e drawing time: t3m (± 1month) after start of IMP infusion

^f where applicable

7.1.1. Visit 1: Screening

Successfully screened subjects may be re-screened if necessary. Visit 1 procedures shall be performed within 24 hours; the order of these procedures shall be as follows:

- 1) Informed consent must be obtained prior to conducting any procedure that would not have been performed as part of normal subject care
- 2) date of birth, gender, race, general medical and surgical history (including pre-/concomitant medication for the last 3 months) will be recorded.
- 3) physical examination including measurement of body weight, pulse rate and blood pressure and assessment of heart, lung and abdomen will be performed.
- 4) ECG examination
- 5) Baseline TCD examination (acoustic window required for eligibility!)
- 6) clinical biochemistry, clinical haematology (incl. assessment of bleeding according to RE-LY study group criteria), coagulation and urinalysis
- 7) Urine pregnancy tests are to be performed for all eligible women of childbearing potential (WOCBP).
- 8) Assessment of eligibility criteria
- 9) Eligible patients only: Cerebral DWI-NMR (may be performed any time prior to treatment)

Randomisation:

Once all screening examination results are available and indicate that the patient is eligible for the study, patients are allocated to a treatment arm by **stratified randomisation**. Stratification factors are listed in section 6.1.7 p.22.

7.1.2. Visit 2: Treatment

- Physical examination/ vital signs
- Review of concomitant medication
- The trial participant will be given the opportunity to report adverse events (AE) spontaneously, a general prompt will also be given, all adverse events will be followed up until resolution or stabilisation
- Assessment of neurological status (MRS, Barthel Index, NIH Stroke Scale)
- Before administration of study medication, in vitro bleeding time PFA100 / PFA200 and platelet aggregation assay (response to collagen, ADP and TRAP)
- Before administration of study medication, a blood sample for detection of anti-Revacept antibodies will be collected (negative control)
- Pharmacokinetic blood sampling (for approximately 20 % of patients)
 - **t0** prior to IMP administration,
 - **t 0.5h** 30 mins (\pm 5 mins) after start of IMP infusion
 - **t 6h** 6 h (\pm 1 hr) after start of IMP infusion
- **Administration of study medication** will be performed by intravenous infusion for 20 minutes; the time of administration must be recorded.

7.1.3. Visit 3: 24 hrs after treatment (between 2 hrs and 46 hrs after treatment)

- Physical examination/ vital signs
- Review of concomitant medication

- Assessment of AEs
- TCD RECORDING
- ECG examination
- clinical biochemistry, clinical haematology (incl. assessment of bleeding according to RE-LY study group criteria), coagulation and urinalysis
- in vitro bleeding time PFA100 PFA200 and platelet aggregation assay (response to collagen, ADP and TRAP)
- Pharmacokinetic blood sampling (for approximately 20 % of patients)
 - **t24h** 24 hours (\pm 4 hrs) after start of IMP infusion

7.1.4. Visit 4: CEA / intervention (3 days after treatment, -69 hrs / + 5 days)

- Physical examination/ vital signs
- Review of concomitant medication
- Assessment of AEs
- in vitro bleeding time PFA100 /PFA200 and platelet aggregation assay (response to collagen, ADP and TRAP)

THEREAFTER CEA SURGERY OR OTHER INTERVENTIONS CAN BE PERFORMED WITHOUT DELAY

- Pharmacokinetic blood sampling (for approximately 20 % of patients)
 - **T3d** 3 days (\pm 48 hrs) after start of IMP infusion

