As for all antiplatelet drugs, it cannot be entirely excluded at this stage of development that Revacept could potentially increase bleeding propensity. Especially the likelihood of bleeding problems might occur in combination with multiple anti-thrombotic or antiplatelet drugs. In order to keep this risk low, concomitant oral anticoagulation and antiplatelet drugs other than anti-thrombotic monotherapy with Aspirin or Clopidogrel are prohibited in this study.

The immunogenicity of Revacept is judged to be considerably low, as its components are naturally occurring in the human body and should hence be recognised as 'self'. As for all therapeutic proteins, there is residual risk for Revacept triggering an aberrant immune reaction. Potential allergic responses may produce mild symptoms such as skin rashes and flue-like symptoms but also severe and potentially life-threatening reactions such as anaphylactic shocks. In order to minimise the risk of acute allergic reactions, patients with a history of allergic responses to intravenously administered drugs will be excluded from study participation. Furthermore, all patients will remain under medical supervision for 24 hours after receiving study medication.

Although the risk for production of anti-drug antibodies is low for single dose application, anti-Revacept autoantibodies could potentially cross-react with circulating platelets. For minimisation of this risk, patients with a known history of thrombocytopenia will not be

allowed to participate in this study. Furthermore, platelet counts and bleeding time will be closely monitored throughout the trial and blood samples for determination of anti-drug antibodies will be collected before and 3 months after exposure to study treatment.

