7.2.2. Physical examination

Body height will be measured at visit 1. Body weight, heart rate, blood pressure will be recorded at each study visit. The heart rate will taken by feeling the pulse, unless an electrocardiogram is scheduled for the corresponding visit. Blood pressure will be measured once on both arms auscultatorily while the subject is seated, first after 5 minutes of physical and emotional rest. Furthermore, physical examination of heart, lung and abdomen will be performed and any signs of peripheral oedema or ascites will be assessed.

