#### **8.5.1 Vital signs**

Vital signs were assessed at Screening (Visit 1, Baseline) and Visit 2 to Visit 6.

Results of

Statistical Analysis Plan  
Test product: Revacept  
EudraCT number: 2011-001006-10  
Date 10.06.2019

- vital signs
  - Weight
  - Blood pressure systolic and diastolic (right arm / left arm)

will be summarized by visit by means of descriptive statistics. Change from baseline in weight, heart rate, systolic and diastolic blood pressure will be summarized by means of statistics and compared between treatment groups using the Wilcoxon test.

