### **8.5.2 Physical examination**

Physical examination was assessed at Screening (Visit 1, Baseline) and Visit 2 to Visit 6.

Results of assessment of

- heart
- lung
- abdomen
- oedema

will be described presenting number and percent of patients with abnormal findings at post-baseline visits and with normal values at baseline (Screening, Visit 1) and summarized by means of frequency tables.

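### Visit 2 vital signs and examination findings have no stated time relative to the infusion, yet the SAP analyses them against a Visit 1 baseline as later values

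*Protocol*

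**What the plan says.** **Protocol, treatment visit.** Section 7.1.2 includes "Physical examination/ vital signs" with no time attached. In the same list the platelet tests, the antibody sample and the first pharmacokinetic draw are expressly pre-dose, and two further draws are timed from the start of the infusion. For the infusion itself, "the time of administration must be recorded".

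**Protocol, general rule.** Section 7.2.2 states "Body weight, heart rate, blood pressure will be recorded at each study visit" and "Blood pressure will be measured once on both arms auscultatorily while the subject is seated". Neither sentence sets a pre- or post-infusion point, and no pre/post pair is required at Visit 2.

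**Protocol, next visit.** Visit 3 (7.1.3), which again includes vital signs and examination, is placed "24 hrs after treatment (between 2 hrs and 46 hrs after treatment".

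**SAP, vital signs.** Section 8.5.1 states "Vital signs were assessed at Screening (Visit 1, Baseline) and Visit 2 to Visit 6". Results are summarised by visit, and change from baseline is compared between groups with a Wilcoxon test.

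**SAP, physical examination.** Section 8.5.2 names the same visits and counts patients with "abnormal findings at post-baseline visits and with normal values at baseline (Screening, Visit 1".

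**Risk and supervision.** Protocol section 2 names allergic reactions, up to anaphylactic shock, as a risk of the infused protein, and says that "all patients will remain under medical supervision for 24 hours after receiving study medication".

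**The concern.** Vital signs are a listed safety endpoint in both documents. A table headed Visit 2, showing change from baseline by treatment group, will naturally be read as the haemodynamic picture on the day of dosing. If the readings were taken before the infusion, the table compares two pre-dose values. Any difference between arms then reflects chance, and the absence of a difference says nothing about the drug. If sites differed in practice, a drug effect would be diluted by an unknown amount.

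The examination count has the same weakness. A finding that appears between screening and the start of the infusion would be counted as new after baseline although the patient had not yet been dosed. Such change is plausible without any drug effect. These patients had a recent cerebrovascular event, and Protocol 5.2.2 provides for treatment of hypertension. Visit 1 procedures must fit within 24 hours (7.1.1), but no maximum gap from Visit 1 to Visit 2 is stated.

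**Working it through.** The plan gives no figure to reproduce here. The check is a reading of the sections side by side, plus arithmetic on the visit windows.

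**1. When is the first reading that must be post-dose?**
- Visit 3 is at 24 h ± 22 h: 24 − 22 = 2 h and 24 + 22 = 46 h, which matches the text of 7.1.3.
- Visit 4 is at 3 days, with −69 h allowed: 72 − 69 = 3 h at the earliest, so it does not open before Visit 3.
- Hence no vital signs are required between the start of the 20-minute infusion and 2 h. The first required set may fall as late as 46 h.

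**2. Does another scheduled item fill the gap?**
- The 0.5 h pharmacokinetic draw is at 30 ± 5 min from the start of a 20-minute infusion, which is 5 to 15 min after its end. It covers only about 20% of patients and has no vital signs attached.
- ECG heart rate is recorded at Visits 1, 3, 5 and 6 (SAP 8.5.3), not at Visit 2.

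**3. What can the Visit 2 value be?** Let p be the share of Visit 2 readings taken after the infusion, and d the true acute shift between an active arm and placebo in such readings. Assume p is the same in each arm, as blinding should ensure. The expected between-arm difference in mean change from Visit 1 is p × d.

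| Practice at Visit 2 | p | Expected difference | What the table shows |
|---|---|---|---|
| All readings pre-dose | 0 | 0 | Change before dosing; no drug effect |
| Mixed across sites or patients | between 0 and 1, unknown | between 0 and d | Diluted effect, dilution unknown |
| All readings post-dose | 1 | d | What the SAP layout implies |

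Neither document fixes p. Only the last row supports reading Visit 2 as on-treatment change.

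**4. How much of the analysis is affected?** Visits 2 to 6 are five visits, and one of the five has this ambiguity. Visits 3 to 6 are after treatment by definition.

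**5. Can the values be sorted afterwards?** Infusion start and end times are documented (SAP 8.3). Neither document requires a clock time for the vital signs, so sorting depends on whether the CRF or source records hold one.

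**The case against.** The strongest reply is that the list in 7.1.2 carries no timing. Only Visit 1 has a binding order of procedures, and the Visit 2 list also puts the 0.5 h and 6 h post-infusion draws ahead of the administration item. Where the protocol wants a pre-dose measurement it says so, and it does not say so for vital signs. This stands. A reader might infer from the list order that Visit 2 readings are certainly pre-dose, and so that the endpoint could never show an acute effect. The documents do not support that: a post-infusion reading at Visit 2 is not excluded, and Visit 3 may take place from 2 h. What remains is the ambiguity, which does not depend on list order.

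A second reply is that acute reactions are captured elsewhere: 24-hour supervision, the adverse-event prompt and spontaneous reporting (7.1.2, 8.3), continuous assessment of toxicity (7.3), and the recording of significant worsening on any safety assessment (8.7). This also stands. It would be wrong to infer that an anaphylactic reaction would go unrecorded.

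Third, 8.5.1 does not itself call Visit 2 post-baseline. That term is in 8.5.2, and SAP 7.6 describes the safety data as purely descriptive. Both are true. But 8.5.1 names Visit 1 as baseline, lists Visit 2 among the visits that follow, and compares change between groups. Descriptive tables still need correct labels.

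Two further inferences should be avoided. A nearer baseline might be expected to gain precision, but the documents give no correlations, so no size can be put on it. The supervision period might be assumed to have produced timed blood-pressure readings, but the protocol says only that patients are supervised.

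**Conclusion.** The point holds as a gap in timing and labelling. Protocol 7.1.2 and 7.2.2 leave the single Visit 2 set of vital signs and findings untimed, while SAP 8.5.1 and 8.5.2 analyse it against Visit 1 among the later visits. Visit 2 change and newly abnormal findings therefore cannot be relied on as evidence for or against an acute infusion effect.

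The extent is one of five later visits in two sets of safety tables. Supervision, adverse-event recording and the results from Visit 3 onward are untouched. The conclusion rests on the protocol and SAP alone. The CRF and the study-drug handling instructions are not available and may fix the timing. If they show that all Visit 2 readings were post-dose, the SAP layout is sound for Visit 2 and only needs to say so. The point is modest, but worth acting on because the remedy is nearly free and prevents a misleading treatment-day table.

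**What to change.** Before unblinding, for which the data review meeting in SAP 7.2 is the natural occasion, reconcile Protocol 7.1.2 and 7.2.2 with SAP 8.5.1 and 8.5.2 on when the Visit 2 values were taken. Then amend the SAP:

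- **Baseline:** the last value before the start of infusion. This is Visit 2 where that value is documented as pre-dose, and Visit 1 otherwise. Use the recorded infusion start time and any recorded measurement time.
- **Pre-dose Visit 2 values:** leave them out of the post-baseline comparisons in 8.5.1 and the newly abnormal counts in 8.5.2.
- **Visit 2 values that cannot be timed:** report them separately as untimed, not as post-dose change.

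The cost is a little extra programming, and some Visit 2 values may prove impossible to classify. No new measurement is proposed. The SAP, dated 10.06.2019, describes enrolment in the past tense, so the remedy has to work with data already collected.
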